11.2 Conditions during the trial

11.2.1 Medical care

For any adverse events, a causal or symptomatic treatment according to standard medical practice should be provided if deemed necessary by the investigator. The medical care given to, and medical decisions made on behalf of the subjects must be the responsibility of a qualified physician.

See the guidance in the investigator's brochure for precautions and the handling of emergencies.

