12.1.2 Prior and concomitant medication

All medication requiring prescriptions (including oral contraceptives), over-the-counter medication, traditional medicine, phytotherapy, and any other treatment ingested or applied to the skin or mucosal surface within 14 days prior to enrollment and up to the end of the trial must be recorded in the CRF. Toothpastes and mouthwashes need not be documented.

For the purposes of data reporting by the site, all medication used 14 days prior to enrollment and up to the time of surgery is considered prior medication. Concomitant medication is all medication not stopped before surgery or newly added thereafter.

Any addition to or change in dosage, regimen, or route for concomitant medications during the trial must be recorded in the CRF as a new entry.

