
Adverse events occurring in the Enrollment Period but before first administration of an IMP and worsening on or after IMP administration will be documented as new adverse events.

Definition of outcome at the time of last observation

The outcome at the time of last observation will be classified as:

- Recovered/Resolved
- Recovering/Resolving
- Not recovered/Not resolved
- Recovered/Resolved with sequelae.
- Fatal
- Unknown (unknown should only be used, if at the time of the last visit for a subject in a trial, the outcome of the adverse event is unknown to the investigator, e.g., because the subject is lost to follow-up).

In the event of irreversible congenital anomalies, the choice “not resolved” should be used. “Fatal” should only be used when death is possibly related to the adverse event (note: the causal relationship of the IMP to the adverse event is not to be considered for this decision). If there is more than 1 adverse event, only the adverse event leading to death (possibly related) will be attributed with the outcome “fatal”.

Definition of countermeasures

“Countermeasures” will be defined as:

None:	No countermeasure given.
Newly started medication:	A newly started medication or change in dose or route of application of a medication due to the adverse event (to be listed on the prior/concomitant medication page) that is used as a countermeasure.

Trial discontinuation:	It was necessary to discontinue the subject from the trial due to the adverse event.
Other:	All other countermeasures, e.g., physical therapy, surgery.

Except for none, multiple countermeasures for 1 adverse event can be recorded.

Classification of action taken with IMPs when an adverse event occurs:

- Dose reduced.
- Drug interrupted.
- Drug withdrawn.
- Dose not changed.
- Not applicable.
- Unknown.

Classification of causation

The causal relationship of an adverse event to IMPs will be classified using the following terminology. The given criteria for each term are for consideration and are neither exhaustive nor required to be fulfilled in total for the selection of the respective term:

Terms for classification of causation	Criteria for the selection of causality classification terms
Conditional/ Unclassified:	Additional data for a proper assessment are under examination.
Unassessable/ Unclassifiable:	The available data cannot be judged because information is insufficient or contradictory, and cannot be supplemented or verified.

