7.12 Prior and Concomitant Medications

Verbatim terms on case report forms will be mapped to Anatomical Therapeutic Chemical (ATC) class and Generic Drug Names using the World Health Organization (WHO) dictionary (version March 2016).

For the purposes of data reporting by the site, all medications used 14 days prior to enrollment and up to the time of surgery are considered prior medications. Concomitant medications are all medications not stopped before start of surgery or newly added thereafter. Prior medications and concomitant medications will be summarized separately for each treatment by WHO ATC level 1 term, ATC level 3 term and generic drug name, with frequency and percentage of subjects in each dosing arm using each prior medication and each concomitant medication. At each level of subject summarization, a subject is counted once if he/she reported one or more medications at that level. Each summary will be ordered alphabetically by each level of ATC class and by generic drug name within each level of ATC class. Prior and concomitant medications will also be listed separately with these elements as well as the verbatim drug name.

The overall summary and subsets of prior and concomitant medications will be provided for the Safety Set, FAS and PPS.

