Adverse events will be coded to System Organ Class (SOC) and preferred term using MedDRA (version 19.0). The tabular summaries will be provided for AEs, with the number and percentage of subjects reporting each type of event presented by each treatment group and placebo. If a subject reports the same preferred term more than once, it is counted only once within that category. Further, for a given tabulation, the preferred term will only be counted once at its worst severity and strongest relationship to treatment.

Any adverse event which occurs after first administration of the IMPs or pre-existing adverse event which worsens (adverse change in intensity, frequency, or quality) after first administration of the IMPs compared to the complaint present before first intake of the IMPs is considered as a TEAE.

TEAEs will be summarized for each treatment group by SOC and Preferred Term. Additional summaries by time to onset, duration, intensity, relationship to IMP (Related/Not Related), outcome, expectedness, and countermeasures will also be produced. Events reported as "Conditional/Unclassified", "Assessable/Unclassifiable", "Possible", "Probable/Likely", or "Certain" will be included in the Related category. Events reported as "Unlikely Related" or "Not Related" will be included in the Not Related category. Expectedness will be assessed by the sponsor. An unexpected adverse event is one where the nature or intensity is not consistent with the information in the investigator's brochure. Definition of intensity (mild, moderate, or severe) and countermeasures (none, newly started medication, trial discontinuation, or other) is described in the protocol Section 12.3.1.

Subjects with SAEs will be summarized and additionally listed. Special attention will be given to those subjects who discontinue treatment due to an adverse event or who experience a severe adverse event or SAE.

The incidence of all adverse events and TEAEs leading to premature discontinuation from treatment will be presented descriptively.

Selected subset of adverse events

Selected adverse events of interest will be summarized in a separate table:

- Nausea
- Vomit
- Abdominal Pain
- Gastrointestinal Bleeding
- Dizziness
- Hypotension

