14.3.1.8	Treatment-Emergent Adverse Events Leading to Dose Interruption by System Organ Class and Preferred Term (Safety Set)
14.3.1.9	Treatment-Emergent Adverse Events Leading to Study Drug Withdrawal by System Organ Class and Preferred Term (Safety Set)
14.3.1.10	Treatment-Emergent Adverse Events Leading to Dose Reduction, Dose Interruption, or Study Drug Withdrawal by System Organ Class and Preferred Term (Safety Set)
14.3.1.11	Pre-Treatment Adverse Events by System Organ Class and Preferred Term (Safety Set)
14.3.1.12	Day 1 Treatment Emergent Adverse Events by System Organ Class and Preferred Term (Safety Set)
14.3.1.13	Post-Treatment Adverse Events by System Organ Class and Preferred Term (Safety Set)
14.3.1.14	Treatment-Emergent Adverse Events by SOC and Preferred Term (Safety Set Subgroup: Age < median)
14.3.1.15	Treatment-Emergent Adverse Events by SOC and Preferred Term (Safety Set Subgroup: Age ≥ median)
14.3.1.16	Treatment-Emergent Adverse Events by SOC and Preferred Term (Safety Set Subgroup: Female)
14.3.1.17	Treatment-Emergent Adverse Events by SOC and Preferred Term (Safety Set Subgroup: Male)
14.3.1.18	Treatment-Emergent Adverse Events by SOC and Preferred Term (Safety Set Subgroup: Mestizo)
14.3.1.19	Treatment-Emergent Adverse Events by SOC and Preferred Term (Safety Set Subgroup: Non-Mestizo)
14.3.1.20	Treatment-Emergent Adverse Events by SOC and Preferred Term (Safety Set Subgroup: Baseline Pain Intensity Moderate)
14.3.1.21	Treatment-Emergent Adverse Events by SOC and Preferred Term (Safety Set Subgroup: Baseline Pain Intensity Severe)
14.3.1.22	Treatment-Emergent Adverse Events by SOC and Preferred Term (Safety Set Subgroup: Using Concomitant Medication at Any Time During the Study)
14.3.1.23	Treatment-Emergent Adverse Events by SOC and Preferred Term (Safety Set Subgroup: Not Using Concomitant Medication at Any Time During the Study)

Table Number	Table Description
14.3.1.24	Treatment-Emergent Adverse Events by SOC and Preferred Term in at least 20% of Subjects in any Treatment Group (Safety Set)
14.3.2.1	Treatment-Emergent Serious Adverse Events by System Organ Class and Preferred Term (Safety set)
14.3.2.2	Treatment-Emergent Fatal Serious Adverse Events by System Organ Class and Preferred Term (Safety Set)
14.3.2.3	Treatment-Emergent Non-Fatal Serious Adverse Events by System Organ Class and Preferred Term (Safety Set)
14.3.4.1	Hematology Values at Enrollment Visit Conventional Units (Safety Set)

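### The concomitant-medication subgroup in two adverse event tables can be set by the adverse events those tables count, so users and non-users would differ even with no true relation

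*SAP*

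**What the plan says.** SAP Appendix C lists Table 14.3.1.22 ("Safety Set Subgroup: Using Concomitant Medication at Any Time During the Study") and Table 14.3.1.23 ("Safety Set Subgroup: Not Using Concomitant Medication at Any Time During the Study"). Both present TEAEs by System Organ Class and Preferred Term.

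SAP 7.12 sets the scope of the flag: "Concomitant medications are all medications not stopped before start of surgery or newly added thereafter". Protocol 12.1.2 has the same scope: "Concomitant medication is all medication not stopped before surgery or newly added thereafter". Neither makes an exception for drugs given because of an adverse event.

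Protocol 12.3.1, under the definition of countermeasures, covers a medication started or changed "due to the adverse event (to be listed on the prior/concomitant medication page) that is used as a countermeasure". Protocol 11.2.1 foresees such treatment: for any adverse event "a causal or symptomatic treatment according to standard medical practice should be provided if deemed necessary by the investigator". SAP 10.1 defines the TEAEs being counted, beginning "Any adverse event which occurs after first administration of the IMPs or pre-existing adverse event which worsens".

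The body of the SAP does not describe these two subgroups. Sections 8.5 and 9.2.3 cover only TOTPAR subgroups, and 10.1 names no safety subgroup. The table titles are the only specification.

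**The concern.** A subgroup should be fixed before the outcome it is used to describe. The other TEAE subgroups in Appendix C (age, sex, Mestizo or not, baseline pain intensity) meet that condition. The medication pair does not, because part of the flag is set after dosing and one route into it is treatment of a TEAE.

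Two misreadings are possible. Across the two tables, a higher event rate in users could be taken as a sign that other medication worsens tolerability of the trial drugs. Within either table, arms could be compared as if the comparison were randomised. If arms differ in how often events are treated with a drug, the split itself differs by arm and that protection is lost. SAP 10.1 singles out nausea, vomiting and dizziness as events of interest, so the arm pattern of such events will be looked at.

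**Working it through.** **Reasoning from the definitions.** A TEAE treated with a drug puts that drug on the concomitant medication page (Protocol 12.3.1). Anything on that page added after surgery is concomitant medication (SAP 7.12, Protocol 12.1.2). The flag covers the whole study. Such a subject must therefore appear in Table 14.3.1.22 and cannot appear in Table 14.3.1.23. Nothing in either document restricts the flag to use before first dose or before event onset.

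**Size.** The plan states no figure for these tables, so there is none to reproduce. The inputs below are assumptions, except the 200 subjects per arm (SAP 4):

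- a = true TEAE risk, the same whether or not other medication is used
- b = share of subjects using concomitant medication for other reasons
- t = share of subjects with a TEAE who receive at least one drug for it, taken as unrelated to b

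TEAE rate in users = a[b + (1 − b)t] / [b + (1 − b)at]

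TEAE rate in non-users = a(1 − t) / (1 − at)

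Non-users per arm = 200 × (1 − b)(1 − at)

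For any t above 0, with a and b strictly between 0 and 1, the first rate exceeds a and the second is below a. The direction therefore does not depend on the values chosen. With a = 0.20:

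| b | t | Users | Non-users | Non-users per 200 |
|---|---|---|---|---|
| 0.30 | 0.25 | 0.095/0.335 = 28.4% | 0.15/0.95 = 15.8% | 133 |
| 0.30 | 0.50 | 0.130/0.370 = 35.1% | 0.10/0.90 = 11.1% | 126 |
| 0.90 | 0.25 | 0.185/0.905 = 20.4% | 0.15/0.95 = 15.8% | 19 |
| 0.90 | 0.50 | 0.190/0.910 = 20.9% | 0.10/0.90 = 11.1% | 18 |

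Over a wider grid (a 0.2 to 0.4, b 0.2 to 0.9, t 0.1 to 0.5) the artificial gap runs from 1.8 to 41.7 percentage points:

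- a = 0.2, b = 0.9, t = 0.1: 20.2% − 18.4% = 1.8
- a = 0.4, b = 0.2, t = 0.5: 66.7% − 25.0% = 41.7

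**Arm comparison inside the non-user table.** Take two arms with the same true risk, a = 0.30, that differ only in how often events are treated. At t = 0.1 the non-user rate is 0.27/0.97 = 27.8%. At t = 0.5 it is 0.15/0.85 = 17.6%. The difference of about 10 points comes from the split alone.

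**With a flag fixed before dosing.** Treatment of the event no longer moves anyone, t drops out, and both rates equal a (for example 20.0% and 20.0%).

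**The case against.** The strongest reply is that nothing inferential rests on these tables. SAP 10 says safety measures are summarised descriptively. No interaction test, user versus non-user comparison or between-arm test is planned within them, and they are 2 of 24 tables numbered 14.3.1.x. The titles state openly that the flag covers the whole study. This stands, and it limits the point to a low-priority improvement.

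The documents also offer partial ways to see the problem. SAP 10.1 promises TEAE summaries by countermeasure (although Appendix C lists no table with that title), and Listings 16.2.7.1 and 16.2.4.11 show adverse events and concomitant medications. These help a careful reader trace treated events, but they do not remove the artefact from the two tables.

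A reader might infer that the subgroup is simply the outcome under another name. The documents do not support that. The flag also captures oral contraceptives (named in Protocol 12.1.2) and antibiotics (allowed by Protocol 1.5). Treatment of an adverse event is one route into the user group, and nothing shows that it is the main one.

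A reader might also take 35% against 11% as the expected size. It is one corner of an assumed range. If most subjects take something else, the user table is almost undistorted and the distortion sits in a very small non-user group.

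**Conclusion.** The point holds as a flaw of definition in two descriptive tables. Following the plan as written is expected to push the user rate up and the non-user rate down whenever an otherwise unmedicated subject has a drug-treated TEAE. Arm comparisons within either table lose the protection of randomisation if arms differ in treated events.

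The direction follows from the documents; the size does not. At an assumed 20% true risk with a quarter to half of affected subjects treated, the gap is about 13 to 24 points if 30% use other medication (28.4 − 15.8 = 12.6; 35.1 − 11.1 = 24.0). It is about 5 to 10 points if 90% do (20.4 − 15.8 = 4.6; 20.9 − 11.1 = 9.8), with fewer than 20 non-users in a 200-subject arm.

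It would be wrong to infer that the trial's safety conclusions are compromised. The overall TEAE table (14.3.1.2) does not use the flag, and neither does any efficacy test.

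**What to change.** In SAP 10.1, define the flag for Tables 14.3.1.22 and 14.3.1.23 as at least one medication started before the day of first IMP dose and not stopped before surgery. Dates are enough for this. Add a drug started on the day of dosing only where the record shows it was started before the first dose. Surgery and first dose fall on the same day, and Protocol 12.1.2 does not require medication start times, so that order will not always be known. The definition should also cover missing start dates, because SAP 5.3 sets a completely missing start date to the date of first dose.

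State that drugs recorded as adverse event countermeasures, and rescue ibuprofen or ketorolac, do not set the flag. Rescue drugs have their own listings (16.2.5.3 and 16.2.5.4), but the literal definition of concomitant medication would include them. Retitle both tables to match.

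The cost is one definition and two titles, with no new assessments. There is a small downside: drugs first started after dosing, such as post-operative antibiotics, would no longer count as concomitant use in these two tables. They remain in Tables 14.1.8.1 to 14.1.8.3 and in Listing 16.2.4.11.
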